#### 9.2.1.2 Serious Adverse Events

For more detailed instructions on SAE reporting refer to the SAE Form Completion Guidelines contained in section 5 of the Investigator Site File (ISF). AEs defined as serious and which require reporting as an SAE should be reported on an SAE Form. When completing the form, the Investigator will be asked to define the causality and the severity of the AE which should be documented using the CTCAE version 4.0. On becoming aware that a patient has experienced an SAE, the Investigator (or delegate) must complete, date and sign an SAE Form. The form should be faxed together with a SAE Fax Cover Sheet to the Trial Office using one of the numbers listed below as soon as possible and no later than 24 hours after first becoming aware of the event:

To report an SAE, fax the SAE Form with an SAE Fax Cover Sheet to: [name] or [name]

On receipt the Trial Office will allocate each SAE a unique reference number. This number will be transcribed onto the SAE Fax Cover Sheet which will then be faxed back to the site as proof of receipt. If confirmation of receipt is not received within 1 working day please contact the Trial Office. The SAE reference number should be quoted on all correspondence and follow-up reports regarding the SAE. The SAE Fax Cover Sheet completed by the Trial Office should be filed with the SAE Form in the ISF. For SAE Forms completed by someone other than the Investigator the Investigator will be required to countersign the original SAE Form to confirm agreement with the causality and severity assessments. The form should then be returned to the Trial Office in the post and a copy kept in the ISF. Investigators should also report SAEs to their own Trust in accordance with local practice.

#### 9.2.1.3 Provision of follow-up information

Patients should be followed up until resolution or stabilisation of the event. Follow-up information should be provided on a new SAE Form (refer to the SAE Form Completion Guidelines for further information).

#### 9.2.2 Trial Office

On receipt of an SAE Form seriousness and causality will be determined independently by a Clinical Coordinator. An SAE judged by the Investigator or Clinical Coordinator to have a reasonable causal relationship with the trial medication will be regarded as a Serious Adverse Reaction (SAR). The Clinical Coordinator will also assess all SARs for expectedness. If the event meets the definition of a SAR that is unexpected (i.e. is not defined in the Investigator Brochure) it will be classified as a Suspected Unexpected Serious Adverse Reaction (SUSAR).

# 9.2.3 Reporting to the Competent Authority and main Research Ethics Committee

# 9.2.3.1 Suspected Unexpected Serious Adverse Reactions (SUSARs)

The Trial Office will report a minimal data set of all individual events categorised as a fatal or life threatening SUSAR to the Medicines and Healthcare products Regulatory Agency (MHRA) and main Research Ethics Committee (REC) within 7 days. Detailed follow-up information will be provided within an additional 8 days. All other events categorised as SUSARs will be reported within 15 days.

#### 9.2.3.2 Serious Adverse Reactions

The Trial Office will report details of all SARs (including SUSARs) to the MHRA and main REC annually from the date of the Clinical Trial Authorisation, in the form of a Development Safety Update Report (DSUR).

#### 9.2.3.3 Adverse Events

Details of all AEs will be reported to the MHRA on request.

# 9.2.3.4 Other safety issues identified during the course of the trial

The MHRA and main REC will be notified immediately if a significant safety issue is identified during the trial. Details of all SUSARs and any other safety issue which arises during the course of the trial will be reported to Principal Investigators. A copy of any such correspondence should be filed in the ISF.

#### 9.2.4 Manufacturer of Investigational Medicinal Product (IMP)

All SAEs will be reported to the manufacturer of the IMP, AstraZeneca, by fax within 24 hours of receipt at the SCART Trial Office.

### 10 DATA HANDLING AND RECORD KEEPING

# 10.1 Data Collection

The Case Report Form (CRF) will comprise of the following forms:

Standard Forms	Summary of data recorded	Schedule for submission
Eligibility Form.	Confirmation of eligibility and satisfactory	Within 2 weeks of
	staging investigations where necessary.	registration.
Registration Form.	Patient details and Registration Number.	Within 2 weeks of
		registration.
Baseline Assessment	Details of baseline assessments inc. physical	Within 2 weeks of
Form.	exam, clinical photography, blood pressure,	registration.
	ECG, baseline LVEF, ophthalmological	
	assessment, haematology and biochemistry,	
	tumour biopsy, HIV-1 viral load, CD4 count,	
	PBMC collection (for sub study). HAART	
	regimen.	
Treatment Cycle	Details of 21-day cycle inc. physical exam,	End of every cycle. Within
Forms (separate	clinical photography, blood pressure, ECG,	1 week.
forms for cycles 1-6).	haematology and biochemistry, toxicities.	
Adverse Events	List of all adverse events.	End of every cycle. Within
Form.		2 weeks
Concomitant	List of concomitant medication.	End of every cycle. Within
Medications Form.		2 weeks.
Treatment	Details of additional treatment cycles post	End of every additional
Continuation Forms	completion of 6 cycles.	cycle. Within 1 week.
Off Study Form	Details of haematology and biochemistry	Within 2 weeks.
	assessments, potential ECHO, tumour	
	response and no. of completed cycles	
30-Day Post	Details of potential biochemistry and	Within 2 weeks.
Discontinuation	ECHO/MUGA assessments, plus follow up of	
Follow-Up Form	Adverse Events and Concomitant	
	Medications.	
12-Weekly Follow-up	Details of physical exam and clinical	Annually following
Form.	photography (every 12 weeks for 12 months	completion of treatment.
	post end of treatment).	
Ad Hoc Forms		

Additional ECHO/MUGA Scan	Details of ECHO or MUGA (to be performed in patients with symptoms (AEs) suggestive of cardiac impairment).	Within 2 weeks.
Additional Ophthalmologic Exam	Details of ophthalmologic exam (to be performed in patients experiencing visual disturbances)	Within 2 weeks.
Additional Haematology/ Clinical Chemistry Assessments	Haematology and biochemistry assessments performed until all AEs are resolved to baseline upon completion of treatment	Within 2 weeks.
Serious Adverse Event Form.	Details of SAEs	Immediately (within 24 hours) upon notification of an SAE.
Post Treatment Adverse Event Follow-Up Form	Record AEs that have not resolved to baseline at 30 Day Post-Discontinuation visit.	Within 2 weeks.
Pregnancy Notification Form.	Record pregnancy of patient or patient's partner	Immediately upon notification of pregnancy.
Treatment Discontinuation Form.	Date and reason for discontinuation.	Within 1 week.
Death Form.	Date and cause of death.	Immediately upon notification of patient's death.
Withdrawal Form.	thdrawal Form. Date and reason for patient withdrawal.	
Deviation Form.	Completed in the event of deviation from the protocol.	Immediately upon discovering deviation.
Cycle 1 Forms		
Copy of Adverse Events Form *	List of all adverse events.	End of Cycle 1. Within 1 week
Copy of Concomitant Medications Form *	List of concomitant medication.	End of Cycle 1. Within 1 week

\*Adverse Events Form and Concomitant Medications Form must be photocopied and sent to the Trial Office within 1 week of the End of Cycle 1 (Cycle 1 Day 22 visit).

The CRF must be completed, signed/dated and returned to the Trial Office by the Investigator or an authorised member of the site research team (as delegated on the Site Signature and Delegation Log) within the timeframe listed above.

Entries on the CRF should be made in ballpoint pen, in blue or black ink, and must be legible. Any errors should be crossed out with a single stroke, the correction inserted and the change initialled and dated. If it is not obvious why a change has been made, an explanation should be written next to the change. Data reported on each form should be consistent with the source data or the discrepancies should be explained. If information is not known, this must be clearly indicated on the form. All missing and ambiguous data will be queried. All sections are to be completed before returning.

In all cases it remains the responsibility of the Investigator to ensure that the CRF has been completed correctly and that the data are accurate. The completed originals should be sent to the Trial Office and a copy filed in the ISF. Trial forms may be amended by the Trial Office, as appropriate, throughout the duration of the trial. Whilst this will not constitute a protocol amendment, new versions of the form must be implemented by participating sites immediately on receipt.

# 10.2 Archiving

It is the responsibility of the Principal Investigator to ensure all essential trial documentation and source records (e.g. signed ICF, ISFs, Pharmacy Files, patients' hospital notes, copies of CRFs etc) at their site are securely retained for at least 15 years after the end of the trial or following the processing of all biological material collected for research, whichever is the later. Do not destroy any documents without prior approval from the CRCTU Document Storage Manager.

### 11 QUALITY MANAGEMENT

#### 11.1 Site Set-up and Initiation

All sites will be required to sign a Clinical Study Site Agreement prior to participation. In addition all participating Investigators will be asked to sign the necessary agreements and supply a current CV to the Trial Office. All members of the site research team will also be required to sign the Site Signature and Delegation Log, which should be returned to the Trial Office. Prior to commencing recruitment all sites will undergo a process of initiation. Key members of the site research team will be required to attend a meeting covering aspects of the trial design, protocol procedures, Adverse Event reporting, collection and reporting of data and record keeping. Sites will be provided with an Investigator Site File and a Pharmacy File containing essential documentation, instructions, and other documentation required for the conduct of the trial. The Trial Office must be informed immediately of any change in the site research team.

#### 11.2 On-site Monitoring

Monitoring will be carried out as required following a risk assessment and as documented in the SCART Quality Management Plan. Additional on-site monitoring visits may be triggered for example by poor CRF return, poor data quality, low SAE reporting rates, excessive number of patient withdrawals or deviations. If a monitoring visit is required the Trial Office will contact the site to arrange a date for the proposed visit and will provide the site with written confirmation. Investigators will allow the SCART trial staff access to source documents as requested.

# 11.3 Central Monitoring

Trials staff will be in regular contact with the site research team to check on progress and address any queries that they may have. Trials staff will check incoming Case Report Forms for compliance with the protocol, data consistency, missing data and timing. Sites will be sent Data Clarification Forms requesting missing data or clarification of inconsistencies or discrepancies.

Sites may be suspended from further recruitment in the event of serious and persistent non-compliance with the protocol and/or Good Clinical Practice (GCP), and/or poor recruitment. Any major problems identified during monitoring may be reported to the Trial Management Group and the relevant regulatory bodies. This includes reporting serious breaches of GCP and/or the trial protocol to the main Research Ethics Committee (REC) and the Medicines for Healthcare products Regulatory Agency (MHRA).

# 11.4 Audit and Inspection

The Investigator will permit trial-related monitoring, audits, ethical review, and regulatory inspection(s) at their site, providing direct access to source data/documents. Sites are also requested to notify the Trial Office of any MHRA inspections.

#### 11.5 Notification of Serious Breaches

In accordance with Regulation 29A of the Medicines for Human Use (Clinical Trials) Regulations 2004 and its amendments the Sponsor of the trial is responsible for notifying the licensing authority in writing of any serious breach of:

- The conditions and principles of GCP in connection with that trial or;
- The protocol relating to that trial, within 7 days of becoming aware of that breach

For the purposes of this regulation, a "serious breach" is a breach which is likely to effect to a significant degree:

- The safety or physical or mental integrity of the subjects of the trial; or
- The scientific value of the trial

Sites are therefore requested to notify the Trial Office of a suspected trial-related serious breach of GCP and/or the trial protocol. Where the Trial Office is investigating whether or not a serious breach has occurred sites are also requested to cooperate with the Trial Office in providing sufficient information to report the breach to the MHRA where required and in undertaking any corrective and/or preventive action.

#### 12 END OF TRIAL DEFINITION

The end of trial is defined as 18 months after closure to recruitment to allow for completion of translational research.

This definition allows completion of the secondary end-point of progression free survival rate at 6 months from commencing treatment. Patients will continue to be followed up beyond 6 months with data collected by the CRCTU to 12 months for supporting evidence for future trial planning. This will allow sufficient time for the completion of protocol procedures, data collection and data input. The Trial Office will notify the MHRA and main REC that the trial has ended and will provide them with a summary of the clinical trial report within 12 months of the end of trial.

Patients responding on selumetinib will be offered to continue on treatment. Patients who have been shown to derive benefit from the selumetinib and HAART combined therapy at one year should be continued on this regimen in an extension study as long as their risk: benefit analysis, in the opinion of the treating physician, favours the continuation of treatment and with approval from AstraZeneca. The number of treatment cycles completed and progression free survival data will be collected by the Trial Office 12 months after the last patient completes study treatment to provide supporting evidence of response for future trial development.

After closure of the trial with the MHRA the Sponsor is no longer required to notify the MHRA and main REC of changes of Principal Investigator. However, sites should continue to notify the Trial Office of changes in Principal Investigator by completing and returning (where required) an Investigator Registration Form together with a current signed and dated CV.

The Trial Office will notify the MHRA and main REC that the trial has ended at the appropriate time and will provide them with a summary of the clinical trial report within 12 months of the end of trial.

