Patients who continue to respond to selumetinib following completion of 6 cycles of therapy will be offered the option of continuing selumetinib. In this instance a clinical investigator at sites should email the SCART Trial Office, outlining the clinical benefit experienced by the patient when the patient has reached the C5D22/C6D1 visit. This will be forwarded to AstraZeneca for approval. The approval will then be communicated to sites. Patients who have been shown to derive benefit from the selumetinib and HAART combined therapy at one year should be continued on this regimen as long as their risk: benefit analysis, in the opinion of the treating physician, favours the continuation of treatment and with approval from AstraZeneca. In this instance sites should contact the SCART Trial Office.

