# 3.2 Phase II

Patients will be recruited in a single-arm study at the RPTD, in order to determine objective tumour response using AIDS Clinical Trials Group Oncology Committee (ACTG) criteria (see Appendix 1). Patients recruited to the RPTD during phase I will be included in the phase II study. KS will be evaluated using clinical photographs of target lesions and bi-dimensional measurements every 3 weeks and/or CT imaging of assessable disease sites every 6 weeks during treatment. As in phase I, patients who continue to respond to selumetinib following completion of 6 cycles of therapy will be offered the option of continuing selumetinib. Patients who have been shown to derive benefit from selumetinib and HAART combined therapy at one year should be continued on this regimen as long as there has been no disease progression and their risk: benefit analysis, in the opinion of the Chief Investigator and treating physician, favours the continuation of treatment and with approval from AstraZeneca. To continue treatment beyond 6 cycles sites should contact the SCART Trial Office as described in section 3.1. Patients' HAART regimen should not be changed for their first 3 months on the trial (i.e. until after the C4D22/C5D1 visit) unless clinically necessary. If deemed clinically necessary, sites should contact the SCART Trial office to facilitate discussion with the Chief Investigator and Clinical Co-Investigators.

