### 7.2 Treatment Schedule

Six cycles, each of 21 days, will be given unless disease progression or unacceptable toxicity is encountered. Patients who are responding after six cycles of selumetinib will be offered the option of continuing on selumetinib in combination with HAART. Patients who have had no disease progression and have been shown to derive benefit from the selumetinib and HAART combined therapy at one year should be continued on this regimen in an extension of the study as long as their risk: benefit analysis, in the opinion of the Chief Investigator and treating physician, favours the continuation of treatment and with approval from AstraZeneca. However, if after one year there is disease progression, treatment

should be discontinued and the patient should come off study. It should be noted that there is no compassionate use or access to selumetinib once off study.

Patients may also discontinue protocol therapy in the following instances:

- Intercurrent illness which would in the judgment of the investigator affect patient safety, the ability to deliver treatment or the primary study endpoints
- Request by patient

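### Sections 12 and 3.1 omit the no-progression and Chief Investigator conditions that sections 3.2 and 7.2 set for selumetinib beyond one year

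*Protocol*

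**What the plan says.** Four sections of the protocol govern treatment beyond one year.

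- **Section 12 (End of Trial Definition).** The starting condition is benefit: "Patients who have been shown to derive benefit from the selumetinib and HAART combined therapy at one year should be continued". Continuation then holds "in an extension study as long as their risk: benefit analysis, in the opinion of the treating physician" favours it, and with AstraZeneca approval. Neither absence of progression nor the Chief Investigator is mentioned. The continuation is placed in an extension study.
- **Section 3.1 (Phase I).** The same conditions apply: benefit at one year, and a risk:benefit view that "in the opinion of the treating physician, favours the continuation of treatment and with approval from AstraZeneca".
- **Section 3.2 (Phase II).** Continuation holds "as long as there has been no disease progression and their risk: benefit analysis, in the opinion of the Chief Investigator and treating physician", again with AstraZeneca approval.
- **Section 7.2 (Treatment Schedule).** Eligible patients are "Patients who have had no disease progression and have been shown to derive benefit from the selumetinib and HAART combined therapy at one year". The Chief Investigator and the treating physician must both be in favour, and AstraZeneca must approve. The continuation is described as an extension of this study. The section then adds: "However, if after one year there is disease progression, treatment" is to stop and the patient is to come off study.

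Section 12 goes on to say that the number of cycles completed and PFS data will be collected as supporting evidence of response for planning later trials. Section 2.2.2 calls the same items supportive data.

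**The concern.** All four statements are current text, and a site may consult any of them. Sections 7.2 and 12 carry no restriction to phase I or phase II, so both apply to the same patient. When that patient is thought to be benefiting but meets the progression criteria, one section says to continue and the other says to stop.

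At stake is mainly how long a patient receives an investigational drug after progression, and who has to agree to it. A site could follow one section faithfully and depart from the other. A secondary matter is the supportive count of cycles completed, whose content depends on which section was followed.

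**Working it through.** The protocol gives no figure for this point, so the check is a comparison of conditions, followed by a check of which outcomes the conflict can reach.

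**1. Conditions side by side**

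| Condition for treatment after one year | 3.1 | 12 | 3.2 | 7.2 |
|---|---|---|---|---|
| Benefit shown at one year | yes | yes | yes | yes |
| Treating physician in favour | yes | yes | yes | yes |
| AstraZeneca approval | yes | yes | yes | yes |
| No disease progression | not stated | not stated | yes | yes |
| Chief Investigator in favour | not stated | not stated | yes | yes |
| Stop and leave study on later progression | not stated | not stated | not stated | yes |
| Limited to one phase | phase I | no | phase II | no |

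**2. Where the answers differ.** Take a patient with benefit shown at one year, a favourable treating physician and AstraZeneca approval.

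- No progression, Chief Investigator in favour: sections 7.2 and 12 both continue treatment.
- No progression, Chief Investigator not in favour: section 12 continues; the conditions of 7.2 are not met.
- ACTG progression, treating physician still in favour: section 12, read as written, continues; section 7.2 stops treatment.

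**3. Whether the third case can arise.** Appendix 1 counts as progression any new lesion, growth of 25% or more in existing lesions, a change in character of 25% or more of skin or oral lesions, or new or increasing tumour-associated oedema or effusion. A single new lesion is enough, even if the marker lesions have shrunk. A physician could therefore still see overall benefit in a patient who meets the criteria.

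**4. Which outcomes can be affected**

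- Primary outcome: best response to the end of cycle 6 (sections 7.10.3 and 13.2.2). 6 × 21 = 126 days, or 126 / 7 = 18 weeks.
- Secondary outcome: PFS rate at 6 months from the start of treatment (section 2.2.2).
- The disputed rule starts at one year: 365.25 / 21 = 17.4 cycles.

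Both windows close before one year. As a context check, the Simon rule in section 13.1.2 (stop at 1 or fewer responses in 16; active at 5 or more in 25) was computed by exact binomial. It gives a type I error of 0.0951 at a 10% response rate (stated limit 0.10) and power of 0.9030 at 30% (stated 0.90). That design is consistent and untouched. Section 7.10.8 measures PFS until the progression criteria are met, so treatment after progression cannot lengthen a PFS time. What remains is treatment exposure and the supportive cycle count.

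**The case against.** The strongest defence is that the treatment section governs dosing. Section 7.1 gives selumetinib unless there is progression, and section 7.2 expressly stops it. Section 12 defines the end of the trial, and its paragraph on continuation opens with patients who are responding. Silence there about progression is not permission to treat through it. This largely stands: a reader might infer that patients with ACTG progression may stay on drug at the treating physician's sole discretion, and the protocol does not support that. Sections 12 and 3.1 also require benefit at one year and AstraZeneca approval, and 7.2 points the other way. But section 12 says benefiting patients should be continued, lists its own conditions and does not refer to 7.2, so the contradiction remains.

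A second defence is that section 3.1 concerns phase I, which is complete, so its difference from 3.2 may be intended. That is fair, and the weight rests on 7.2 against 12. Section 3.1 is not irrelevant, since section 3.2 sends sites there for the procedure beyond 6 cycles.

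A reader might also infer that calling the continuation an extension study removes the longest-treated patients from the trial's data. The protocol answers this. Section 10.1 provides Treatment Continuation Forms after every additional cycle, and section 12 itself has the Trial Office collect cycles and PFS data.

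Finally, it is tempting to ask that cycles be counted only up to progression. That is a reporting preference about a supportive exposure count, and it does not correct an error.

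**Conclusion.** The concern holds as an internal contradiction. Sections 12 and 3.1 leave out two conditions that 3.2 and 7.2 impose, and 7.2 and 12 conflict directly for a patient judged to benefit who meets ACTG progression. They also describe the status of the continuation differently.

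The effect on the primary response, the Simon decision and 6-month PFS is nil. The effect on exposure after progression and on the supportive cycle count cannot be sized from the protocol, which does not say how many patients would progress after one year or how long they might continue. The conclusion rests on reading section 12 as an operative instruction, which its wording supports. The point deserves correction because it concerns when an investigational drug is stopped. It does not threaten the trial's efficacy conclusion.

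The amendment log lists the progression and Chief Investigator clarification for sections 3.2 and 7.2 only. That fits 3.1 and 12 having been left unaligned, but the finding does not depend on it.

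**What to change.** Reconcile sections 3.1, 3.2, 7.2 and 12 into one continuation rule that states:

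- whether progression bears on continuation, and how;
- who must agree;
- whether the continuation is part of this study or a separate one.

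State the rule in one place and have section 12 refer to it without restating the conditions. Which clinical rule applies is for the sponsor and investigators to decide.

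The cost is amendment wording only. No new data, assessments or patients are needed, and the sample size and planned analyses do not change.
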